6.4 Visit 7 Follow up

Patients will receive a telephone call at week 13 for reassessment. Interval clinical history will be obtained, all adverse events, medication list and alcohol and other substance use will be detailed. PACS score, modified telephone version of MMSE and West Haven HE score will be calculated. Case Report Form will be completed.

6.5 Visit 8 Follow up

Patients will receive a telephone call at week 24 for reassessment. Interval clinical history will be obtained, history of any serious adverse events, medication list and alcohol and other substance use will be detailed. PACS score, modified telephone version of MMSE and West Haven HE score will be calculated. Case Report Form will be completed. Final blood tests will be requested.

	Screening/ Enrollment day	Treatment Period													
		W1	W2	W3	W4	W5	W6	W7	W8	W9	W10	W11	W12	W13	W24
Test/Procedure Name	(D1)														
Study Visit	x													x	
Follow-Up Phone Calls		x	x	x	x				x					x	x
Physical Exam	x													x	
Complete blood count	x													x	x
Electrolytes	x				x				x				x		x
Creatinine	x				x				x				x		x
Urea	x												x		x
Total Bilirubin	x				x				x				x		x
Direct bilirubin	x												x		x
INR	x				x				x				x		x
Urine Ethyl Glucuronide	x				x				x				x		x
Albumin	x												x		x
AST, ALT, alkaline phosphatase	x												x		x
Child Pugh Score	x												x		x
West Haven HE Score	x												x	x	x
MMSE	x	x	x	x	x				x				x	x	x
Med Review	x	x	x	x	x				x				x	x	x
Pennsylvania Alcohol Craving Scale	x	x	x	x	x				x				x	x	x

Adverse event evaluation	x	x	x	x	x			x			x	x	x
Alcohol consumption documentation	x	x	x	x	x			x			x	x	x

7 Statistical Plan

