Study duration will be six months. During the study, patients will complete monthly MELD-Na labs and receive a phone call weekly for the first month, then monthly for a total of 3 months. Urine ethyl glucuronide will be done at enrollment and once monthly. Patients will then have a follow up visit at 12 weeks, with labs, urine ethyl glucuronide, vital signs and physical exam. During telephone assessments and at the follow up visit, patients will be asked about potential side effects and hepatic decompensation. Other variables to be collected at enrollment and at the 3 month visit include Child-Pugh score, West Haven grading of HE, vital signs at enrollment and current medications. At enrollment, during phone calls and at the follow up visit, patients will be asked standardized questions to assess for HE based on the abbreviated telephone version of the mini-mental state examination (MMSE). Follow up telephone visits at 13 and 24 weeks will be conducted, primarily to monitor for adverse events and alcohol relapse.

The Pennsylvania Alcohol Craving Scale (PACS) will be applied before treatment initiation, weekly for the first month on treatment, then monthly thereafter. This will include the need severity scale (mild, moderate, severe) at baseline and at each assessment by phone call and in clinic.

Alcohol use relapse will be monitored. Any amount of alcohol use as revealed during follow-up considered a relapse event. Alcohol use will be captured and categorized as none, slip (no longer drinking at most recent follow up) or sustained alcohol use (minimum 100 days drinking). Slips and sustained alcohol use will be categorized as binge drinking, frequent drinking, or both (binge drinking as more than 6 units/day for men and 4 units/day for women and frequent drinking as alcohol use in 4 or more days/week regardless of quantity per day) (Lee et al., 2018).

Basic descriptive statistics and a qualitative analysis will be performed. Analyses will be performed using SPSS 25 (Chicago, IL). Results will not contain any patient-specific information.

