8.1 Definitions

Unanticipated Problems Involving Risk to Subjects or Others (UPIRTSO)

Any unanticipated problem or adverse event that meets the following three criteria:

- Serious: Serious problems or events that results in significant harm, (which may be physical, psychological, financial, social, economic, or legal) or increased risk for the subject or others (including individuals who are not research subjects). These include: (1) death; (2) life threatening adverse experience; (3) hospitalization - inpatient, new, or prolonged; (4) disability/incapacity - persistent or significant; (5) breach of confidentiality and (6) other problems, events, or new information (i.e. publications, DSMB reports, interim findings, product labeling change) that in the opinion of the local investigator may adversely affect the rights, safety, or welfare of the subjects or others, or substantially compromise the research data, **AND**
- Unanticipated: (i.e. unexpected) problems or events are those that are not already described as potential risks in the protocol, consent document, not listed in the Investigator's Brochure, or not part of an underlying disease. A problem or event is "unanticipated" when it was unforeseeable at the time of its occurrence. A problem or event is "unanticipated" when it occurs at an increased frequency or at an increased severity than expected, **AND**
- Related: A problem or event is "related" if it is possibly related to the research procedures.

Adverse Event

An untoward or undesirable experience associated with the use of a medical product (i.e. drug, device, biologic) in a patient or research subject.

Serious Adverse Event

Adverse events are classified as serious or non-serious. Serious problems/events include;

- death
- life threatening adverse experience
- hospitalization
- inpatient, new, or prolonged; disability/incapacity
- persistent or significant disability or incapacity

and/or per protocol may be problems/events that in the opinion of the investigator may have adversely affected the rights, safety, or welfare of the subjects or others, or substantially compromised the research data.

All adverse events that do not meet any of the criteria for serious, will be regarded as **non-serious adverse events**.

Adverse Event Reporting Period

For this study, the study treatment follow-up period is defined as 12 weeks following the last administration of study treatment.

Preexisting Condition

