8.2 Recording of Adverse Events

At each contact with the subject, the study team must seek information on adverse events by specific questioning and, as appropriate, by examination. Information on all adverse events should be recorded immediately in the source document, and also in the appropriate adverse event section of the case report form (CRF). All clearly related signs, symptoms, and abnormal diagnostic, laboratory or procedure results should be recorded in the source document.

All adverse events occurring during the study period will be recorded. The clinical course of each event should be followed until resolution, stabilization, or until it has been ultimately determined that the study treatment or participation is not the probable cause. Serious adverse events that are still ongoing at the end of the study period will be followed up to determine the final outcome. Any serious adverse event that occurs during the Adverse Event Reporting Period and is considered to be at least possibly related to the study treatment or study participation will be recorded and reported immediately.

Adverse events will be classified per the CTCAE Version 5.0, November 27, 2017.

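### Section 6.5 limits the week-24 adverse event history to serious events, contradicting 3.1, 8.2 and the schedule, so non-serious off-drug events after week 13 may be missed or collected inconsistently

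*Combined protocol and SAP*

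**What the plan says.** The two off-drug follow-up calls are described in nearly the same words but with different scope. For week 13, Section 6.4 says "all adverse events, medication list and alcohol and other substance use will be detailed". For week 24, Section 6.5 says "Interval clinical history will be obtained, history of any serious adverse events, medication list and alcohol and other substance use will be detailed".

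Other parts of the plan bear on the week-24 call:

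- Section 3.1 gives the purpose of both calls: "Follow up telephone visits at 13 and 24 weeks will be conducted, primarily to monitor for adverse events and alcohol relapse".
- Section 8.2 sets a rule for every contact: "At each contact with the subject, the study team must seek information on adverse events by specific questioning".
- Section 8.2 also says: "All adverse events occurring during the study period will be recorded". Sections 3.1 and 3.3 put the duration at six months, so week 24 lies inside the study.
- The schedule that follows Section 6.5 has a row labelled "Adverse event evaluation", with no restriction to serious events.
- Section 8.1, under the heading Adverse Event Reporting Period, says: "For this study, the study treatment follow-up period is defined as 12 weeks following the last administration of study treatment".

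Section 3.4 makes adverse event reporting the measure of the primary endpoint and gives no time window. Section 7.2 has the safety data tabulated descriptively and shown overall, with no split between events on and off treatment.

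**The concern.** The visit sections tell staff what to ask at each contact, and Section 6.5 is the only one after baseline that narrows the adverse event question to serious events. For a subject who completes treatment, week 24 is the only scheduled contact after week 13, so no later call can recover what is not asked then.

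If some callers work from 6.5 and others from 8.2, the data for weeks 13 to 24 will depend on who made the call. If all work from 6.5, a single overall safety table will combine a period in which every event was solicited with one in which only serious events were. A reader of that table could not tell whether an absence of non-serious events after week 13 means that none occurred or that nobody asked. In a descriptive study of 10 subjects, one or two subjects more or fewer visibly change a frequency table.

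**Working it through.** The plan states no figure on this point, so there is nothing to reproduce. The check compares the passages and then sizes the interval.

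**1. Scope of the adverse event question, by contact**

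| Contact | Visit text | Scope |
|---|---|---|
| Visits 2-5 (telephone) | 6.2 | adverse events, unrestricted |
| Visit 6 (week 12) | 6.3 | adverse events, unrestricted |
| Visit 7 (week 13) | 6.4 | all adverse events |
| Visit 8 (week 24) | 6.5 | serious adverse events |
| Every contact | 8.2 | adverse events, unrestricted |
| Weeks 13 and 24 | 3.1 | adverse events, unrestricted |

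**2. The schedule row.** The adverse event row lost cells when the PDF was read: it has 13 cells under 15 column heads. It still carries nine marks: five in a run, one alone, then three in a run. The intact MMSE row has nine marks in the same pattern, at enrollment, weeks 1-4, week 8, and weeks 12, 13 and 24. The last adverse event mark therefore reads as week 24. This is an inference from a damaged row, and the contradiction with 3.1 and 8.2 does not depend on it.

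**3. Length of the interval.** Inputs: last dose at about week 12 (6.3), follow-up of 12 weeks after the last dose (8.1), calls at weeks 13 and 24 (6.4, 6.5).

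- End of the follow-up period: 12 + 12 = week 24, the time of the last call.
- Interval covered only by the week-24 call: 24 - 13 = 11 weeks.
- Share of the study: 11/24 = 46%. Share of the post-treatment period: 11/12 = 92%.

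These are shares of calendar time, not of events missed.

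**4. On-drug or off-drug.** Section 5.1 quotes a terminal half-life of 20 to 33 hours. One week is 168 hours. 168/20 = 8.4 half-lives leaves 0.5^8.4 = 0.3%, and 168/33 = 5.1 half-lives leaves 0.5^5.09 = 2.9%. With a last dose at week 12, events arising after week 13 are essentially off-drug.

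**5. Scale, for illustration only.** The documents give no event rate for weeks 13 to 24. Let q be an assumed probability that a subject has at least one non-serious event in that interval. With 10 independent subjects, the chance that at least one is affected is 1 - (1 - q)^10:

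| Assumed q | Expected subjects affected | Chance of at least one |
|---|---|---|
| 5% | 0.5 | 40% |
| 10% | 1 | 65% |
| 20% | 2 | 89% |

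These are subjects whose events would be exposed to loss if 6.5 were followed literally. They do not predict how many would be lost.

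**The case against.** The strongest reply is that the plan taken as a whole already requires the right thing. Section 8.2 is mandatory at every contact, 3.1 states the purpose of the call, and the schedule appears to mark an unrestricted evaluation. Section 6.5 itself takes an interval clinical history and completes the case report form, which Section 3.7 says includes adverse events without restriction. Section 9.3 makes that form the primary collection instrument, and the form is an attachment that is not available here. What callers will actually ask therefore cannot be known. Section 8.1 also has unresolved events followed to resolution, so events already open at week 13 are not lost. All of this stands. It reduces the likelihood of loss but does not remove the contradiction.

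Four stronger readings are tempting, and the documents do not support them:

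- **The plan collects only serious events at week 24.** That is true of one sentence in 6.5, not of the plan.
- **Section 8.1 requires all events to be recorded for 12 weeks off treatment.** It sets only the length of follow-up. The one rule tied by name to that reporting period, in 8.2, concerns serious events at least possibly related to treatment or participation. The duty to record all events comes from 8.2 read with the six-month duration.
- **Hepatic decompensation would go unseen.** Section 6.5 calls for West Haven and MMSE scoring and requests blood tests at week 24, and the schedule marks bilirubin, INR, albumin, creatinine and Child-Pugh score there. Much of it would be picked up.
- **A comparison of on-drug with off-drug rates would be distorted.** No such comparison is planned.

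**Conclusion.** The contradiction is real. Its consequence is conditional: if staff follow 6.5, non-serious off-drug events arising in weeks 13 to 24, which is 11 of 24 study weeks, may be missed or collected inconsistently. The overall safety table would then mix two standards of ascertainment. On-treatment collection and the week-13 call are unaffected, and no sample size or error rate is involved.

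A reader might infer that the primary endpoint is under-ascertained. The documents do not establish that. The endpoint has no stated time window, other sections require full collection, and the case report form cannot be seen.

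The conclusion assumes a last dose at about week 12. If three months of treatment runs to about week 13 (3 x 365/12 = 91 days), the interval is still 11 weeks, but its first days would include drug washout. The correction is worth making because the data feed the primary endpoint, no later scheduled contact can recover them, and the change costs very little.

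**What to change.** Reconcile the passages by changing the week-24 text in 6.5 from serious to all adverse events, so that it agrees with 6.4, 8.2 and the schedule. Check that the case report form used for that call carries the same question.

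In 7.2, tabulate events with onset after the last dose separately from on-treatment events. The adverse event worksheet in 8.3.1 already records the date of each event, so no new data item is needed.

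If the narrower scope was intended, then 3.1, 8.2 and the schedule would have to change instead, and the safety table would need a note that non-serious events were not solicited after week 13. That is the weaker option, since the call is already being made.

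The cost is a few words in the protocol, a slightly longer call that is already scheduled, and one extra table split. No visit, test or subject is added.

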7.1 Sample Size Determination

As the study is a phase IIa safety trial, no power analysis was completed.

7.2 Statistical Methods

Descriptive Statistics

Univariate descriptive statistics and frequency distributions will be calculated, as appropriate for all variables. Baseline values for demographic, clinical, and outcome variables (primary and secondary) will be tabulated.

Safety analyses will be conducted using all subjects, and presented overall. Safety data will be analyzed using descriptive statistics and tabulation.

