Acamprosate has not been evaluated formally in individuals with AUD and liver disease. It is an N-methyl-D-aspartate glutamate receptor antagonist approved by the Food and Drug Administration to aid in maintaining abstinence in individuals with alcohol dependence (Frye et al., 2016). Acamprosate has an unclear mechanism of action, although it is thought that its effect on decreased alcohol craving intensity is mediated through a reduction in glutamate levels (Frye et al., 2016). The efficacy of acamprosate has been demonstrated in several meta-analyses, most recently exhibiting a number needed to treat of 12 to prevent return to any drinking (Jonas et al., 2014; Rosato et al., 2015). Acamprosate is not metabolized by the liver and thus has been considered as a potential therapeutic option in those with liver disease. However, as acamprosate antagonizes the glutamate receptor, there have been concerns it may increase the risk of hepatic encephalopathy. Previously, a single dose of acamprosate 666 mg was administered to 12 patients with Child-Pugh A or B cirrhosis with no identifiable induction of subclinical hepatic encephalopathy; however, transient diastolic hypotension was noted (Delgrange et al., 1992). No further studies on acamprosate have been performed in individuals with liver disease.

To evaluate the safety of acamprosate in individuals with AUD and alcohol-related liver disease, an initial pilot study in five patients with a Model for End Stage Liver Disease Sodium (MELD-Na) score less than 20 will be conducted. If no safety concerns are identified, the study will then

be performed in five patients with MELD-Na scores of 20 or more. If again no safety concerns are identified, a larger, placebo-controlled efficacy study is planned and will be submitted as a separate protocol.

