This study is a phase IIa trial of the safety of acamprosate in treating AUD in alcohol-related liver disease. Subjects will be screened for eligibility at outpatient clinic visits and during hospitalizations; interested qualified subjects will be consented and offered participation in this trial. At study enrollment, initial MELD-Na score must be less than 20 for the five individuals enrolling in the first phase of the pilot safety assessment. The second phase of the pilot safety assessment will include individuals with a MELD-Na of 20 or more at enrollment. Once consent has been obtained, baseline characteristics will be established and then patients will be initiated on acamprosate treatment. Acamprosate will be administered for three months, during which time, patients will complete monthly blood work, weekly telephone assessments for the first month, followed by telephone assessments and urine testing on a monthly basis thereafter. A final clinic visit for evaluation and collection of lab samples will be conducted at the end of the study at 3 months. Patients will be contacted by telephone at weeks 13 and 24 after study enrollment for final follow up assessments off of study medication.

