4.4 Early Withdrawal of Subjects

4.4.1 When and How to Withdraw Subjects

Patients will be withdrawn from the study prior to study completion if:

1. Subjects elect to withdraw consent
2. Subject is found to be ineligible for the protocol as per the Inclusion/Exclusion criteria.
3. Subjects experience a serious adverse event felt to possibly be related to acamprosate administration as determined by PI and/or DSMB.
4. Failure of the subject to comply with protocol requirements.
5. Exhibition of unacceptable toxicity which would make it difficult or dangerous to comply with further protocol requirements such as study visits, blood draws, etc.
6. There are changes in medical status of the subject such that the Investigator believes that subject safety will be compromised or that it would be in the best interest of the subject to stop participation in the study.

7. Death of the subject.
8. Subjects with a test consistent with pregnancy such as a positive beta-hCG.
9. Subject is lost to follow-up.
10. Any complication that requires prolongation of the hospitalization or change in treatment and in the opinion of the investigator is related to the study drug.

If subjects are withdrawn from the study, they will be replaced to ensure a total of 10 patients complete the study in its entirety. The data collected up until the time of withdrawal from the study will be included in analysis.

Follow up from subjects withdrawn from study treatment will include:

- Clinic visit at time of withdraw from study will be recommended. Beyond risk of returning to alcohol consumption, sudden study treatment termination should not include any subject safety considerations.
- Follow up phone call 3 months after withdrawal from study

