6.1 Visit 1 – Screening/enrollment day

Informed consent will be obtained. Inclusion and exclusion criteria will be evaluated. Collected baseline characteristics will include patient age, sex, race, marital and employment status, education level, social support, presence of children, age of children, underlying liver disease etiology, MELD-Na score, presence of ascites, esophageal varices, spontaneous bacterial peritonitis, diabetes, corticosteroid or other medical treatment for alcoholic hepatitis (Maddrey and Lille scores if relevant), medical comorbidities, prescription and non-prescription medications. With regard to alcohol use, patients will fill out the Alcohol Use Disorder Identification Test (AUDIT) and the following history will be obtained: duration of excess alcohol consumption in years, level of alcohol consumption prior to study enrollment, interval of alcohol abstinence prior to study enrollment, family history of alcoholism, history of alcohol-related legal issues, psychiatric comorbidity (requiring medication, outpatient care or hospitalization), other addictions including smoking and number of prior rehabilitation attempts for alcohol or other addictions. The PACS questionnaire will be administered.

Vital signs and a physical examination will be performed. West Haven HE score will be graded and modified telephone version of MMSE completed. Blood work will be completed including a complete blood count, electrolytes, creatinine, blood urea nitrogen, total bilirubin, direct bilirubin, albumin, INR, AST, ALT and alkaline phosphatase. A urine ethyl glucuronide will be performed. A urine pregnancy test will be conducted before admission into the trial for women of child-bearing potential.

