7.3 Subject Population(s) for Analysis

All subjects that received at least one dose of study drug will be evaluated.

8 Safety and Adverse Events

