A preexisting condition is one that is present at the start of the study. A preexisting condition will be recorded as an adverse event if the frequency, intensity, or the character of the condition worsens during the study period.

General Physical Examination Findings

At screening, any clinically significant abnormality will be recorded as a preexisting condition. At the end of the study, any new clinically significant findings/abnormalities that meet the definition of an adverse event must also be recorded and documented as an adverse event.

Post-study Adverse Event

All unresolved adverse events will be followed by the investigator until the events are resolved, the subject is lost to follow-up, or the adverse event is otherwise explained. At the last scheduled visit, the investigator should instruct each subject to report, to the investigator, any subsequent event(s) that the subject, or the subject's personal physician, believes might reasonably be related to participation in this study.

Abnormal Laboratory Values

Determination of whether worsening of liver biochemical tests is due to the alcohol-related hepatitis or study drug induced liver injury (DILI) is difficult. An AST or ALT increase >500 IU/L would be considered an indication that the patient might have DILI since AST and ALT are typically $< 300-400$ U/L in AH. Such an increase of > 500 IU/L would trigger prompt evaluation and consideration of discontinuation of the study drug. Considering how difficult it is to distinguish potential DILI from worsening of the underlying liver disease, we have incorporated an external adjudication of all suspected DILI events. An increase in MELD-Na score >5 points from baseline, or doubling bilirubin (2 times the baseline level at enrollment) would warrant urgent review by the DSMB.

The study will be **stopped** if three or more patients develop AST or ALT > 500 U/L or as or as determined by the DSMB.

Hospitalization, Prolonged Hospitalization or Surgery

Any adverse event that results in hospitalization or prolonged hospitalization will be documented and reported as a serious adverse event unless specifically instructed otherwise in this protocol. Any condition responsible for surgery will be documented as an adverse event if the condition meets the criteria for an adverse event.

Neither the condition, hospitalization, prolonged hospitalization, nor surgery are reported as an adverse event in the following circumstances:

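### Safety is to be presented only overall, although the study is staged by MELD-Na; add descriptive columns for the two cohorts (minor)

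*Combined protocol and SAP*

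**What the plan says.** Section 7.2 plans descriptive statistics and tabulation for safety and fixes the presentation: "Safety analyses will be conducted using all subjects, and presented overall". Section 7.3 defines a single population: "All subjects that received at least one dose of study drug will be evaluated". The Study Summary and section 3.1 add basic descriptive statistics and a qualitative analysis, and neither names a grouping variable.

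The design is staged. Section 1.1 describes five patients with MELD-Na below 20, followed by five with 20 or more if no safety concern is found. Sections 3, 3.1 and 4.1 repeat the staging: "The second phase of the pilot safety assessment will include individuals with a MELD-Na of 20 or more at enrollment". Section 1.1 then looks beyond this study: "If again no safety concerns are identified, a larger, placebo-controlled efficacy study is planned".

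Three other provisions bear on the table:
- Section 4.4.1 says of withdrawn patients that "they will be replaced to ensure a total of 10 patients complete the study in its entirety".
- Section 6.1 lists MELD-Na among the baseline data: "underlying liver disease etiology, MELD-Na score, presence of ascites".
- Section 3.1 states that the results will carry no information specific to a patient.

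**The concern.** The primary endpoint (section 3.4) is an estimate of the safety profile from adverse event reporting. There is no control group and no test, so the descriptive safety table is the main quantitative result. MELD-Na at enrollment decides who enters when, yet the planned presentation drops it.

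A reader of the final table could not see whether events fell mainly in one MELD-Na cohort or were spread evenly. This applies to serious events too. Under section 8.5 a serious adverse event puts the study on hold, but the study restarts if the DSMB considers the event unrelated, and that event then enters the same pooled count.

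**Working it through.** **Inputs.** Cohort sizes of 5 and 5 come from section 1.1 and the total of 10 from section 3.2; 5 + 5 = 10, so they agree. The plan gives no event rate, alpha or power to reproduce (section 7.1 states that no power analysis was done). All event counts below are therefore assumptions for illustration.

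**Step 1: what a pooled count leaves open.** Let x1/n1 be patients with an event in the MELD-Na <20 cohort and x2/n2 in the ≥20 cohort. The overall column shows (x1 + x2)/(n1 + n2). For an assumed overall 2/10 = 20.0% (exact 95% CI 2.5% to 55.6%):

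| <20 | ≥20 | Overall | ≥20 rate (exact 95% CI) | Overall minus ≥20 rate |
|---|---|---|---|---|
| 0/5 | 2/5 | 2/10 | 40.0% (5.3% to 85.3%) | −20 points |
| 1/5 | 1/5 | 2/10 | 20.0% (0.5% to 71.6%) | 0 |
| 2/5 | 0/5 | 2/10 | 0% (0% to 52.2%) | +20 points |

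The overall column is identical in all three rows. With a one-patient imbalance, 1/5 and 2/5 give 3/10 = 30.0% against a ≥20 rate of 40.0%; 2/5 and 1/5 give the same 30.0% against 20.0%.

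**Step 2: denominators.** Withdrawn patients are replaced and everyone dosed is analysed, so a cohort may exceed five. Section 4.4.1 secures ten completers in total and does not fix the number per cohort. If two replacements fell in the ≥20 cohort (an assumption), 0/5 and 2/7 give 2/12 = 16.7% overall against 2/7 = 28.6%.

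**Step 3: what a split can and cannot do.** Fisher's exact test, 5 against 5, two-sided:
- 0/5 against 2/5: p = 2 × C(5,2)/C(10,2) = 20/45 = 0.44.
- 0/5 against 4/5: p = 2 × C(5,4)/C(10,4) = 10/210 = 0.048.
- Only 0/5 against 4/5, 1/5 against 5/5 (also 0.048) and 0/5 against 5/5 (0.008) reach p ≤ 0.05.
- Power for assumed true rates of 10% and 60% is 22%.

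The split is therefore descriptive only.

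**Step 4: precision, a separate matter.** With no events, the two-sided exact 95% upper limit is 1 − 0.025^(1/n): 52.2% for 0/5 and 30.8% for 0/10. No interval is planned. This affects how a zero is read and does not bias any rate.

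**The case against.** The strongest reply is that the objective is safety in alcohol-related liver disease as a whole, so the pooled proportion answers the question asked. That is correct. The differences in step 1 show what the overall column leaves unseen; they are not errors in it.

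A second reply is that the stages are already looked at separately. The gate in section 1.1 requires a safety judgement on the lower MELD-Na cohort before the higher one opens, and the DSMB charter (section 8.6.1) may specify summaries by stage. The gate does imply a separate look, but section 7 specifies no tabulation for it. The charter could not be checked, and section 7.2 does not refer to it. If the second stage never opens, the overall table is the lower cohort and the point falls away.

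A third is that the qualitative analysis or a patient listing would show the pattern. The qualitative analysis names no grouping. A listing is not a ready substitute, because section 3.1 rules out patient-specific information in the results.

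Four stronger readings are tempting, and the documents do not support them:
- A reader might infer that in-study safety decisions are weakened. The gates, DSMB reviews and stopping rules work on individual cases or counts, and nothing says that the decision on the larger study uses the pooled percentage.
- A reader might infer that a by-cohort table would show whether event rates differ by MELD-Na. Step 3 shows that it could not.
- A reader might infer that pooling understates risk in sicker patients. It can err in either direction or not at all, and the documents give no cohort rates.
- A reader might infer that only non-serious events are affected. The final table pools serious events as well.

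**Conclusion.** The point holds as a minor reporting gap. The planned summary of the primary endpoint would not display events by the variable that stages the study, and no section supplied fills the gap. In the illustrations the overall figure lies from 20 points below to 20 points above the rate in the higher MELD-Na cohort, with no difference when the cohorts are alike. These sizes rest on assumed counts, on both stages being enrolled, and on an unseen charter that may or may not add a summary by stage. The design, the overall estimate and the in-study safeguards stand.

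**What to change.** Replace the sentence in section 7.2 with text to this effect: *Safety will be tabulated by MELD-Na cohort at enrollment (<20; ≥20) and overall, as patients with an event over patients treated in that cohort, for any AE, any SAE, any AE at least possibly related to study drug, and any CTCAE v5.0 grade 3 or higher AE. The comparison is descriptive and no between-cohort test is planned.*

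Rows beyond any AE are needed because that row may be nearly full in this population: "A preexisting condition will be recorded as an adverse event if the frequency, intensity, or the character of the condition worsens". Denominators should be patients dosed, in line with section 7.3 and the replacement rule.

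The grade 3 or higher row needs CTCAE grades on the CRF, and the sections on grading must first be reconciled. Section 8.2 says "Adverse events will be classified per the CTCAE Version 5.0, November 27, 2017", and section 8.5 relies on CTCAE grades. Section 8.3.1, however, mentions a five-level scale and then defines mild, moderate and severe for the CRF.

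Exact 95% intervals are an optional, separable addition.

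The cost is one sentence and two columns, since MELD-Na is already collected at enrollment, plus the wording needed to settle the grading. The downside is a slightly longer table with small cells and, if intervals are added, wide ones.
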